PP	Per Protocol
PPI	Proton Pump Inhibitor
SAE	Serious Adverse Event
SAP	Statistical Analysis Plan
SF	Screen Failure
SUSAR	Suspected Unexpected Serious Adverse Reaction
UADE	Unanticipated Adverse Device Effect
UBT	¹³ C-Urea Breath Test
US	United States (of America)
USA	United States of America

Exalenz Bioscience Ltd.	Last update on: Mar. 12, 2017
Study Title: Clinical Study to Confirm Safety and Accuracy in Detection of H. pylori with ¹³C-Urea Breath Test using the BreathID® Hp and BreathID® Hp Lab Systems in the Pediatric Population	Protocol Number: PED-HP-0616B Version 2.0
Document No.: CSD00092	Page 7 of 59

1. PROTOCOL SYNOPSIS

Protocol Title: *Clinical Study to Confirm Safety and Accuracy in Detection of H. pylori with ¹³C-Urea Breath Test using the BreathID® Hp and BreathID® Hp Lab Systems in the Pediatric Population*

Short Title: Pediatric Hp study

Protocol Reference #: PED-HP-0616B

Version and Date: Protocol v 2.0, March 12, 2017

Phase of Development: Phase III

Sponsor and Study Monitor: Exalenz Bioscience Ltd.

[name]
[name]
[contact]
[contact]

Investigated Disease: *Helicobacter pylori* infection

Study Start Date: Q2 2017

Duration of Study: Approximately 6 months

Investigational Products (IP): *BreathID® Hp System* (K130524) and *BreathID® Hp Lab System* (K162150)

IP Details:

1. The *BreathID® Hp System* (K130524) that uses the approved test kit *IDkit:Hp™ One* in adults, comprised of a nasal cannula and the approved ¹³C-urea/citric acid reagent (NDA-21-314).
2. The *BreathID® Hp Lab System* (K162150) that uses the cleared test kit *IDkit:Hp™ Two*, comprised of two breath sample bags and the approved ¹³C-urea/citric acid reagent (NDA-21-314).

Exalenz Bioscience Ltd.	Last update on: Mar. 12, 2017
Study Title: Clinical Study to Confirm Safety and Accuracy in Detection of H. pylori with ¹³C-Urea Breath Test using the BreathID® Hp and BreathID® Hp Lab Systems in the Pediatric Population	Protocol Number: PED-HP-0616B Version 2.0
Document No.: CSD00092	Page 8 of 59

Study Goal and Rationale:

The goal of this study is to expand the use of the breath test to the pediatric population for safety at the dose being tested, and effectiveness, to gain indication of the test kits in pediatrics. Also, this study will address CDER's request for expansion of the use of the ¹³C-urea and citric acid that is the subject of NDA-21-314, to the pediatric population (ages 3-18¹).

Based on a recent guidance document released by the FDA on June 21, 2016: *Leveraging Existing Clinical Data for Extrapolation to Pediatric Uses of Medical Devices*, the **BreathID® Hp System** and the **BreathID® Hp Lab System**, meet the main criteria needed for extrapolation of the efficacy of clinical data for Pediatric Use:

- a) **Relevancy of Adult Data and Similarity of Response:** The breath test, its kits and the contained test substrate are all well established in the adult population (K130524 and K162150) using the biopsy composite reference method as the gold standard. The *H. pylori* infection is the same in children and adults as *H. pylori* colonize the stomach in humans of all ages. In fact, infection is commonly spread to children in the family. The mechanism of detection for this breath test is by measuring the activity of the *H. pylori* organisms that split urea and are only present in the human stomach. Positive breath testing is indicative of *H. pylori* activity in the subject's stomach, independently of the subject's age. This has been confirmed by individual investigators and other companies (PMA# P1000254) utilizing the composite reference standard⁽¹⁻³⁾.
- b) **Quality of Safety and Effectiveness Data:** The clinical data collected for the clearance of the **BreathID® Hp**

¹ Subjects 18 years of age and older will not be included in this study. The age range of 18-21 was included in the framework of the adult protocols (any adult over 18) to support this cleared indication in the adult population.

Exalenz Bioscience Ltd.	Last update on: Mar. 12, 2017
Study Title: Clinical Study to Confirm Safety and Accuracy in Detection of H. pylori with ¹³C-Urea Breath Test using the BreathID® Hp and BreathID® Hp Lab Systems in the Pediatric Population	Protocol Number: PED-HP-0616B Version 2.0
Document No.: CSD00092	Page 9 of 59

System and the **BreathID® Hp Lab System** breath tests (K130524 and K162150 respectively), were collected in accordance with the ethical principles under Investigational Review Board (IRB) approval consistent with Good Clinical Practice (GCP) and with the applicable regulatory requirements.

This approach was confirmed by FDA through Pre-Sub Q170072.

This study is thus primarily aimed to confirm tolerance and safety of the dose used for the pediatric population. The ¹³C-urea and citric acid (NDA-21-314) are contained in **IDkit:Hp™ One** in the **BreathID® Hp System** (K130524) and **IDkit:Hp™ Two** in the **BreathID® Hp Lab System** (K162150). Additionally the respective means of breath collection, the nasal cannula and breath collection bags contained in the respective kits, will be confirmed for pediatric use.

Although it is believed that the efficacy of the test can be fully extrapolated from the adult data, subject's *H. pylori* status will also be collected as part of this study in order to further support and confirm the efficacy of the breath test in the pediatric population.

The safety of the specific drug substance in children at the dose utilized in the test setting remains to be established in this study. The dose has been proven to be both safe and effective in adults in clinical trials as well as in routine clinical use in more than 150,000 subjects.

Upper endoscopy - Esophagogastroduodenoscopy (EGD) is generally not standard of care for evaluation of children with symptoms associated with *H. pylori* infection. As such, it is difficult to justify performing the procedure which requires sedation only for the research purpose. Children are evaluated for *H. pylori* infection most commonly with stool antigen

Exalenz Bioscience Ltd.	Last update on: Mar. 12, 2017
Study Title: Clinical Study to Confirm Safety and Accuracy in Detection of H. pylori with ¹³C-Urea Breath Test using the BreathID® Hp and BreathID® Hp Lab Systems in the Pediatric Population	Protocol Number: PED-HP-0616B Version 2.0
Document No.: CSD00092	Page 10 of 59

testing. Therefore, this study proposes to test the drug and its dosing in symptomatic children suspected of having *H. pylori* who will undergo both a breath test and an FDA cleared stool test. The stool test has a sensitivity and specificity ranging from 90 to 97%, and comparing the breath test to the stool test results will confirm that the use of this test is reasonable in the target population.

This study will enroll all-comers whether for initial diagnosis or post-eradication testing. It will predominantly (approximately 2/3) enroll children under the age of 12 to confirm drug/dose tolerance and confirm its efficacy. Older children between 12 and 18 years are similar to adults and no more than a third (approximately 1/3) will be enrolled from this age group.

Description of Test:

The ¹³C-Urea Breath Test is performed using a test kit that contains 75mg of non-radioactive ¹³C-urea and citric acid to be dissolved in tap water ("solution").

Exhaled breath will be collected using:

- (1) a nasal cannula for continual passive collection of breath samples from the nose before and after ingestion of the solution, and/or
- (2) two breath sample bags (orally and actively exhaled breath) obtained at two defined time points, before and after ingestion of the solution.

Both exhaled breath collection methods will be performed in parallel, and the subject will ingest the solution only once after baseline breath collection.

The subject's exhaled breath is analyzed and the ratio between ¹³CO₂ and ¹²CO₂ is computed.

The ***BreathID® Hp System*** using the cleared ***IDkit:Hp™ One*** collects breath passively from the subject's nostrils via a nasal cannula whose other end is connected to

Exalenz Bioscience Ltd.	Last update on: Mar. 12, 2017
Study Title: Clinical Study to Confirm Safety and Accuracy in Detection of H. pylori with ¹³C-Urea Breath Test using the BreathID® Hp and BreathID® Hp Lab Systems in the Pediatric Population	Protocol Number: PED-HP-0616B Version 2.0
Document No.: CSD00092	Page 11 of 59

the device via a luer lock connector.

The **BreathID® Hp Lab System** is a modified version of the **BreathID® Hp System**, using **IDkit:Hp™ Two** enabling up to 10 pairs of bags (i.e., 2 bags each from 10 separate patient sampling events, resulting in 10 tests) to be measured consecutively and automatically by means of attaching the bags to a dedicated **Auto Sampler** unit. The bags will be collected and measured by the **BreathID® Hp Lab System** within 14 days from the time of collection.

When using breath sample bags, the initial sample, collected immediately before ingesting the ¹³C-urea/citric acid solution, defines the baseline ratio of ¹³CO₂ to ¹²CO₂. The second sample, collected 15 to 20 minutes following the ¹³C-urea/citric acid solution ingestion, is analyzed to determine changes in the ¹³CO₂/¹²CO₂ ratio.

For both the **BreathID® Hp System** and the **BreathID® Hp Lab System**, the patient is considered *H. pylori* positive when the difference between the ratios exceeds a predefined and previously cleared threshold (in adults) of 5 delta over baseline (DOB).

Comparator Details:

Efficacy of the test can be fully extrapolated from the adult data (as confirmed with FDA through Pre-Submission Q170072). The goal of this study is thus primarily aimed to support expansion of the use of the ¹³C-urea and citric acid that is the subject of NDA-21-314, to the pediatric population (ages 3-18) and to confirm tolerance of the dose used for this target population. The ¹³C-urea and citric acid is contained in **IDkit:Hp™ One** (K130524) in the **BreathID® Hp System** and **IDkit:Hp™ Two** (K162150) in the **BreathID® Hp Lab System**. In addition to safety data that is collected for this study, their *H. pylori* status using the stool antigen test will also be collected as a comparator in order to further support

Exalenz Bioscience Ltd.	Last update on: Mar. 12, 2017
Study Title: Clinical Study to Confirm Safety and Accuracy in Detection of H. pylori with ¹³C-Urea Breath Test using the BreathID® Hp and BreathID® Hp Lab Systems in the Pediatric Population	Protocol Number: PED-HP-0616B Version 2.0
Document No.: CSD00092	Page 12 of 59

and confirm the efficacy of the breath test.

As mentioned above, EGD is not standard of care for evaluation of children with symptoms associated with *H. pylori* infection. They are evaluated for *H. pylori* infection most commonly with stool antigen testing. This study proposes to test the drug and its dosing in symptomatic children suspected of having *H. pylori* who will undergo both a breath test and an FDA cleared stool test. This population is chosen as they are the target population for the breath test and therefore drug use, and their evaluation with the stool test, will confirm that the use of this test is reasonable in the target population. Stool testing detects *H. pylori* antigen in stool specimens and can be used for diagnosis, therapeutic monitoring, and proof of eradication post treatment.

This study will use the Premier Platinum HpSA PLUS (K053335) Enzyme Immunoassay test kit for the detection of *H. pylori* antigen in human stool specimens (Appendix B). It will be tested in a central clinical laboratory.

The stool enzyme immunoassay employs a mixture of monoclonal anti-*H. pylori* antibodies as capture antibody and a mixture of peroxidase-conjugated monoclonal anti-*H. pylori* antibodies as detection antibody. Based on the intensity of color developed, results are reported as *H. pylori* antigen detected, not detected, or indeterminate.

A positive result (antigen detected) is indicative of *H. pylori* infection. A negative result (antigen not detected) indicates absence of *H. pylori* or an antigenic level below the assay limit of detection.

Study Design:

Multi-center, non-randomized, open label study, designed to confirm the safety and the efficacy of ¹³C-urea breath test using the ***BreathID® Hp and BreathID® Hp Lab Systems, as appropriate***, in pediatric subjects and confirm the efficacy of the respective means of breath collection, the nasal cannula

Exalenz Bioscience Ltd.	Last update on: Mar. 12, 2017
Study Title: Clinical Study to Confirm Safety and Accuracy in Detection of H. pylori with ¹³C-Urea Breath Test using the BreathID® Hp and BreathID® Hp Lab Systems in the Pediatric Population	Protocol Number: PED-HP-0616B Version 2.0
Document No.: CSD00092	Page 13 of 59

and breath collection bags, in this population compared to *stool antigen* testing. A central lab will analyze the stool specimens. Children that cannot inflate the breath collection bags adequately may perform the UBT only with nasal cannula. All children will be exposed to the same dose of the non-radioactive ¹³C-urea and citric acid.

Subjects will be enrolled on a walk-in basis. Subjects will be treated only based on the established methods used in the local routine clinical practice. No patient management decisions should be made based on the investigational **BreathID® Hp** and/or **BreathID® Hp Lab System** test outcomes and the investigator and treating physician will remain blinded to the **BreathID® Hp** and/or **BreathID® Hp Lab System** test results until the end of the study.

Study Population: Consecutive pediatric subjects aged between 3 and 18 years evaluated by the physician, or presented by referral from other institutions or physicians who are clinically indicated to undergo *H. pylori* testing and meet study criteria will be enrolled. Distribution of subject's ages will be monitored to assure all age ranges are represented, while predominantly (approximately 2/3) enrolling children under the age of 12 to confirm drug/dose tolerance and confirm its efficacy.

Consent to participate in the study and to undergo the breath test procedures must be obtained from the legal representative/guardian of every subject following a thorough explanation of the study, including the benefits and risks (if any). The majority (approximately 2/3) of the subjects will be from US centers. Assent will also be obtained from those subjects above the age that local regulations require consenting/assenting of the child.

Sites: Up to 8 US sites will participate in this study. Non-US sites may be included.

Exalenz Bioscience Ltd.	Last update on: Mar. 12, 2017
Study Title: Clinical Study to Confirm Safety and Accuracy in Detection of H. pylori with ¹³C-Urea Breath Test using the BreathID® Hp and BreathID® Hp Lab Systems in the Pediatric Population	Protocol Number: PED-HP-0616B Version 2.0
Document No.: CSD00092	Page 14 of 59

Primary Endpoint: Adverse event rate: The safety of the ¹³C-urea/citric acid solution has been previously established in adults and in children in literature⁽¹⁻³⁾. Any adverse event (whether related or not) will be recorded. There are no safety concerns and no adverse events anticipated for the breath test or the stool antigen test beyond those already listed in the respective labels.

Safety Endpoint: Adverse event rate: The safety of the ¹³C-urea/citric acid solution has been previously established in adults and in children in literature⁽¹⁻³⁾. Any adverse event (whether related or not) will be recorded. There are no safety concerns and no adverse events anticipated for the breath test or the stool antigen test beyond those already listed in the respective labels.

Efficacy Endpoints:

- I. Overall agreement in diagnosis (presence/absence of *H. pylori*) between the **BreathID® Hp System** results where breath is collected using **IDkit:Hp™ One** via a nasal cannula applying the 5 DOB threshold and stool antigen outcome in the pediatric population.

- II. Overall agreement in diagnosis (presence/absence of *H. pylori*) between the **BreathID® Hp Lab System** results when analyzing **IDkit:Hp™ Two** breath sample bags using the 5 DOB threshold and the stool antigen outcome in the pediatric population.

Inclusion Criteria: To be eligible to participate in this study, subjects must meet the following inclusion criteria:

- Be older than 3 and younger than 18 years of age
- Present with a clinical indication compatible with *H. pylori* based on the judgement of the treating physician (such as abdominal pain, nausea, diarrhea, reflux, peptic ulcer, dyspepsia, etc., or following treatment for *H. pylori*)
- Subject/Legal guardian (and subject whenever relevant) is willing to sign the Informed Consent/Assent Form
- Naïve to *H. pylori* treatment in the past 6 weeks

Exclusion Criteria: To be eligible to participate in this study, subjects must NOT meet any of the following exclusion criteria:

Exalenz Bioscience Ltd.	Last update on: Mar. 12, 2017
Study Title: Clinical Study to Confirm Safety and Accuracy in Detection of H. pylori with ¹³C-Urea Breath Test using the BreathID® Hp and BreathID® Hp Lab Systems in the Pediatric Population	Protocol Number: PED-HP-0616B Version 2.0
Document No.: CSD00092	Page 15 of 59

- Participation in other interventional trials
- PPI or H₂ blockers within two (2) weeks prior to breath test/stool antigen test
- Pregnant or breastfeeding female
- Allergy to test substrates
- Antibiotics (not related to *H. pylori* eradication) and/or Bismuth preparations within four (4) weeks prior to breath test
- Exposure to any type of anesthesia, analgesics or sedation 24 hours prior to the breath test.
- Exposure to any ¹³C-enriched substance 24 hours prior to the breath test.
- Children 12 years and older – to be excluded after a written notification from the sponsor is received at the site that the limit of 1/3 of the sample size was achieved for this group
- Subjects outside US - to be excluded after a written notification from the sponsor is received at the site that the limit of 1/3 of the sample size was achieved for this group

Exclusion on the day of the UBT: Subject did not fast for the last hour prior to the UBT

Statistical Considerations:

This study is designed to confirm safety for the use of the ¹³C-urea/citric acid solution used in the cleared Exalenz UBT testing using the ***IDkit:Hp™ One*** and/or ***IDkit:Hp™ Two*** as part of ***BreathID® Hp System*** and/or ***BreathID® Hp Lab System*** and to confirm that they have performance measures in the pediatric population similar to that of adults. Due to the fact that esophagogastroduodenoscopy (EGD) is uncommon in pediatrics, the comparator to be used in this trial is stool antigen testing, a common test method used to diagnose and/or confirm eradication of *H. pylori* infection in

Exalenz Bioscience Ltd.	Last update on: Mar. 12, 2017
Study Title: Clinical Study to Confirm Safety and Accuracy in Detection of H. pylori with ¹³C-Urea Breath Test using the BreathID® Hp and BreathID® Hp Lab Systems in the Pediatric Population	Protocol Number: PED-HP-0616B Version 2.0
Document No.: CSD00092	Page 16 of 59

pediatrics.

Sample Size:

The sample size for this study of pediatric subjects with indications for *H. pylori* testing is calculated to allow confirmation of both, the primary and secondary study endpoints. For the safety assessment, with no related SAE's expected, a sample size of 35 evaluable subjects would provide an upper confidence limit with less than or equal to 10% for the 95% two sided confidence limit. In order to support the efficacy endpoints a sample size is calculated through the width of the two-sided 95% confidence interval of the percent overall agreement, such that the lower limit of the confidence interval will be greater than or equal to 75% with a point estimate of 90%.

A total of at least 40 evaluable subjects with no less than 5 positive subjects will be accrued for both breath collection methods. If the minimum of 5 positive subjects is not reached within the first 40 subjects enrolled, enrolment will continue until this minimal number of positive subjects is reached (with evaluable UBT results for both breath collection methods).

This will be sufficient to confirm the safety and the utility of the **BreathID® Hp System** and **BreathID® Hp Lab System** in detecting *H. pylori* infection in pediatric subjects.

Distribution of subject's ages will be monitored to assure all age ranges are represented, while at least two thirds (2/3) of the enrolled children will be under the age of 12.

Site Termination:

A study site may be terminated after appropriate consultation between the study sponsor and the principal investigator. Conditions warranting termination include, but are not limited to:

- Failure of the investigator to enroll subjects at an acceptable rate
- Insufficient adherence to protocol requirements

Exalenz Bioscience Ltd.	Last update on: Mar. 12, 2017
Study Title: Clinical Study to Confirm Safety and Accuracy in Detection of H. pylori with ¹³C-Urea Breath Test using the BreathID® Hp and BreathID® Hp Lab Systems in the Pediatric Population	Protocol Number: PED-HP-0616B Version 2.0
Document No.: CSD00092	Page 17 of 59

- Decision by the study sponsor to suspend or discontinue development of the device and/or kit
- Failure to adhere to GCP
- Sponsor decision

Regulatory Considerations: The current clinical study will require an IDE as the subject receives a drug substance approved for adults but not yet approved for those under 18 years of age.

Study Procedure: The clinical study will be conducted in compliance with this protocol and in accordance with the ethical principles under Investigational Review Board (IRB) and Ethics Committee (EC) approvals consistent with Good Clinical Practice (GCP) and with the applicable regulatory requirements.

- The investigator(s) at each site will sign a Protocol Approval Page (**Appendix A**).
- Patient management will not be affected by the **BreathID® Hp** and/or **BreathID® Hp Lab System** test results and will be based only on the common clinical method used. The investigator and treating physician will remain blinded to the breath test results until the end of the study.
- Physical examination of the subject and recording of demographic data will be completed.
- The stool antigen test will be performed for each subject after at least 2 weeks of refraining from proton pump inhibitors, antimicrobials and bismuth preparations. The test procedure is described in **Appendix B**.
- Within 1 week before or after the stool antigen test and after refraining at least 2 weeks from proton pump inhibitors and 4 weeks from antimicrobials and bismuth preparations, the subjects will perform the UBT by filling two **IDkit:Hp™ Two** breath collection bags, one at each time point (pre-ingestion and 15-20 minutes post-test solution ingestion) and by having breath collected via the **IDkit:Hp™ One** nasal cannula. Subjects unable to fill the breath collection bags will perform the breath test with the nasal

[figure not shown]
Exalenz Bioscience Ltd.	Last update on: Mar. 12, 2017
Study Title: Clinical Study to Confirm Safety and Accuracy in Detection of H. pylori with ¹³C-Urea Breath Test using the BreathID® Hp and BreathID® Hp Lab Systems in the Pediatric Population	Protocol Number: PED-HP-0616B Version 2.0
Document No.: CSD00092	Page 18 of 59

cannula only.

- All bags will be analyzed by a ***BreathID® Hp Lab System*** within 14 days of collection by unmasked personnel at the site or by a selected central lab.
- The breath collected via nasal cannula will be analyzed continually by an on-site ***BreathID® Hp System*** by unmasked personnel.
- Stool specimens will be sent to a central lab. The site coordinator will provide each subject with all supplies needed for collection of the stool specimen. The specimen will be either collected on-site, brought back to the site, brought to a local approved stool collection facility or it may be sent directly to a central laboratory from the subject's residence. A requisition form will be completed. After confirming that each stool antigen sample was sent to the central lab, the study coordinator will complete an entry line in a log documenting the shipment.
- An electronic Case Report Form (CRF) will be completed for each subject. Any additional diagnostic testing performed for the subjects will be recorded.
- Breath test results will remain non-accessible to the investigator. Unmasked site personnel will be trained to assure results are not shared.

Exalenz Bioscience Ltd.	Last update on: Mar. 12, 2017
Study Title: Clinical Study to Confirm Safety and Accuracy in Detection of H. pylori with ¹³C-Urea Breath Test using the BreathID® Hp and BreathID® Hp Lab Systems in the Pediatric Population	Protocol Number: PED-HP-0616B Version 2.0
Document No.: CSD00092	Page 19 of 59

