comparing monoclonal enzyme immunoassay tests (EIA) and rapid immunochromatographic assays (ICA). The sensitivity and specificity of the tests analyzed had a high variation between 48.9%–92.2% and 88.9%–94.4%, respectively, depending on the test format. Best results were obtained for *Premier Platinum HpSA Plus* (which will be used in this study) with sensitivity and specificity of 92.2% and 94.4%, respectively. They conclude that EIA tests are more accurate compared to the currently available ICA-based test, that are fast and easy to use but provide less reliable results⁽¹⁴⁾. A recent meta-analysis conducted by Zhou and colleagues analyzed forty-five studies, including 5931 subjects, and evaluated the test performance of a *H. pylori* stool antigen test in children. The average sensitivity and specificity was 92.1% and 94.1%, respectively⁽¹⁵⁾. In a study conducted in South Korea on 515 subjects comparing the stool antigen test to histology, RUT, ¹³C-Urea breath test and serology, the accuracy of the stool antigen test ranged from 93% to 96%⁽¹⁶⁾. Furthermore, the available stool antigen tests have been shown to be able to distinguish infected from treated subjects^(17, 18), enabling the confirmation of treatment. Degradation of antigens in the intestine and consequent disintegration of epitopes might lead to false negative results. Moreover, the process of sample handling could be difficult for subjects. False negative results may occur when the bacterial load is low, due to proton-pump inhibitors or the recent use of antibiotics or bismuth^(19, 20). As such, there are limitations in eligibility criteria and study procedures in order to reduce the possibility of any potential effect by these factors⁽¹⁰⁾.

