12.2. Exclusion Criteria

To be eligible to participate in this study, subjects must not meet any of the following exclusion criteria:

- Participation in other interventional trials
- PPI or H₂ blockers within two (2) weeks prior to breath test/stool antigen test
- Pregnant or breastfeeding female
- Allergy to test substrates
- Antibiotics (not related to *H. pylori* eradication) and/or Bismuth preparations within four (4) weeks prior to breath test
- Exposure to any type of anesthesia, analgesics or sedation 24 hours prior to the breath test.
- Exposure to any ¹³C-enriched substance 24 hours prior to the breath test.
- Children 12 years and older – to be excluded after a written notification from the sponsor is received at the site that the limit of 1/3 of the sample size was achieved for this group
- Subjects outside US – to be excluded after a written notification from the sponsor is received at the site that the limit of 1/3 of the sample size was achieved for this group

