13.1.3. Stool sample collection visit (Day 1 +/- 7 days)

1. The stool antigen test will be performed within 7 days before or after the UBT and after at least 2 weeks of refraining from proton pump inhibitors & H2 blockers and 4 weeks of refraining from antimicrobials and bismuth preparations. The test procedure is described in Appendix B.
2. Stool specimens will be sent to a central lab. The site coordinator will provide each subject with all supplies needed for collection of the stool specimen. The specimen will be either collected on-site, brought back to the site, brought to a local approved stool collection facility or it may be sent directly to a central laboratory from the subject's residence. A requisition form will be completed. After confirming that each stool antigen sample was sent to the central lab, the study coordinator will complete an entry line in a log documenting the shipment. The name and the address for the central laboratory service provider can be found in the respective documentation
3. Adverse events will be recorded, according to rules of assessment and documentation defined in Section 17 below).

The visit can be combined with the Breath Test visit and/or with the Screening visit and performed on the same day.

For each subject tested, an individual set of electronic Case Report Forms (CRFs) will be completed.

The Sponsor will notify the sites when to commence and stop recruitment.

Exalenz Bioscience Ltd.	Last update on: Mar. 12, 2017
Study Title: Clinical Study to Confirm Safety and Accuracy in Detection of H. pylori with ¹³C-Urea Breath Test using the BreathID® Hp and BreathID® Hp Lab Systems in the Pediatric Population	Protocol Number: PED-HP-0616B Version 2.0
Document No.: CSD00092	Page 41 of 59

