13.1. Schedule of activities and evaluations

Visit	Screening	Baseline Day 1	Stool Testing
Day	Up to 37 days prior to the breath test	0-7	UBT +/- 7 days
Informed consent Including Assent if applicable	X		
Inclusion & exclusion criteria	X	X	X
Demographic information	X		
Medical history information regarding previous H. pylori results	X	X	
Prior and concomitant medications (starting 6 weeks prior to the Stool Test/UBT)	X	X	X
Physical examination including height and weight		X	
Urine pregnancy test		X	
Adverse event assessment		X	X
UBT - ¹³C-Urea Breath Test (cannula & bags)		X	
Stool Testing			X

Note:

Screening visit can be combined with Day 1 visit and performed on the same day.

Stool test visit can be combined with Day 1 visit or screening visit and performed on the same day.

Breath collection bags will be tested within 14 days after UBT visit.

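### The synopsis allows the comparator stool test after 2 weeks off antimicrobials and bismuth, Section 13.1.3 requires 4 weeks, and the exclusion criterion counts back from the breath test only

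*Combined protocol and SAP*

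**What the plan says.** Four parts of the current text (Version 2.0) bear on how long a child must be off antimicrobials and bismuth before giving stool.

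- **Synopsis, Study Procedure.** The stool test is done "after at least 2 weeks of refraining from proton pump inhibitors, antimicrobials and bismuth preparations". One 2-week period covers all three drug classes. The next bullet, on the breath test, separates them: 2 weeks for proton pump inhibitors, 4 weeks for antimicrobials and bismuth.
- **Section 13.1.3, stool visit.** The same stool test requires 2 weeks off proton pump inhibitors and H2 blockers, but "4 weeks of refraining from antimicrobials and bismuth preparations".
- **Exclusion criteria, synopsis and Section 12.2.** A child is excluded for non-eradication antibiotics or for "Bismuth preparations within four (4) weeks prior to breath test". Only the breath test is named. The acid-suppressant criterion in the same list applies "within two (2) weeks prior to breath test/stool antigen test", so it names both tests.
- **Timing.** The synopsis places the breath test "Within 1 week before or after the stool antigen test", and Section 13.1.3 gives the same 7 days either side. The notes to the schedule of activities add: "Stool test visit can be combined with Day 1 visit or screening visit".

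No section says which rule governs if the synopsis and the body differ.

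**The concern.** Stool antigen is the comparator for both efficacy endpoints. Section 4.2 says false-negative stool results may arise "due to proton-pump inhibitors or the recent use of antibiotics or bismuth", and that the eligibility criteria and procedures are restricted for that reason. The protocol thus relies on its washout to protect the comparator, but states that washout in two ways and omits the stool date from the criterion meant to enforce it.

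The Confirmatory Efficacy Analyses section compares each breath system separately with the same stool result. If stool is falsely negative and the breath test stays positive, one child counts as a disagreement for one or both systems. If the drug suppresses both tests, the pair counts as agreement although both are wrong. The first case lowers agreement and the second hides an error.

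There is also a classification problem. The per-protocol set removes major deviations, and Section 14.5.2 does not define major. A sample that satisfies the synopsis and Section 12.2 but breaches Section 13.1.3 could be handled differently by different sites, monitors or analysts.

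**Working it through.** The plan states no figure for the interval from last dose to stool, so there is none to reproduce. The check is day arithmetic.

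**Inputs**

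- L = days from the last non-eradication antibiotic or bismuth dose to the breath test. The exclusion criterion requires L ≥ 28 (4 weeks).
- s = day of stool relative to the breath test, from -7 to +7 (synopsis; Section 13.1.3).
- Required interval from last dose to stool: 14 days in the synopsis, 28 days in Section 13.1.3.
- Eradication therapy has its own 6-week criterion, so it is outside this question.

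**Formula.** Interval from last dose to stool = L + s.

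**Earliest permitted stool sample under each reading**

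| Rules applied | Earliest stool, days after last dose |
|---|---|
| Synopsis stool sentence alone | 14 |
| Exclusion criterion plus the 7-day window | 28 - 7 = 21 |
| All synopsis rules together (L ≥ 28, interval ≥ 14, window 7) | 21 |
| Section 13.1.3 (L ≥ 28, interval ≥ 28) | 28 |

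The literal 14 days cannot occur, because the breath-test criterion already forces 21. The real conflict is 21 days against 28.

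**When the interval falls short.** L + s < 28 requires s < 28 - L:

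- L = 28: short for s = -7 to -1, giving 21 to 27 days. At s = 0 the interval is 28.
- L = 31: short for s = -7 to -4, giving 24 to 27 days.
- L = 34: short only for s = -7, giving 27 days.
- L ≥ 35: never short, since 35 - 7 = 28.

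So the shortfall is 1 to 7 days. It needs a last dose 28 to 34 days before the breath test and stool given before the breath test. Stool on or after the breath-test day always meets 28 days.

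**What one disagreement weighs.** The success rule is an exact two-sided 95% lower limit for overall agreement of at least 75%. For x agreements out of n, that limit is the 2.5% quantile of a Beta(x, n - x + 1) distribution. At the minimum n = 40:

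- 37/40: 79.61%
- 36/40: 76.34%, which agrees with the plan's premise of a 90% point estimate clearing 75%
- 35/40: 73.20%, which fails

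Each endpoint can therefore absorb at most 4 disagreements in 40. This shows the weight of a single discordant child, not the size of this defect.

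**The case against.** The strongest reply is that the protocol read as a whole does not permit day 21. A minimum of 2 weeks is a floor, Section 13.1.3 sets a stricter floor for the same sample, and a site that obeys both waits 28 days. Section 13.1.3 is also the instruction for the stool visit itself. The data for checking compliance are already collected there, since the schedule includes "Prior and concomitant medications (starting 6 weeks prior to the Stool Test/UBT") at that visit. On this view one synopsis sentence needs correcting and the rest is precaution.

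Much of this is fair. The 21-day case does depend on a site working from the synopsis and Section 12.2 without applying Section 13.1.3. A date check at the stool visit is largely possible already. The exposed group is narrow, and nothing in the documents shows that 21 to 27 days differs materially from 28 for non-eradication antibiotics. Efficacy is secondary and, by the protocol's account, extrapolated from adults; the primary safety endpoint is untouched. A false-negative stool beside a positive breath test works against the sponsor's claim.

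It does not remove the contradiction. No section gives Section 13.1.3 precedence. The criteria are rechecked at the stool visit, but the antibiotic criterion applied there refers to the breath-test date. When stool is given at screening, that date still lies ahead. The acid-suppressant criterion beside it shows how the stool test could have been named.

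**Conclusion.** The concern holds. Two current sections set different antimicrobial and bismuth washouts for the comparator sample, and the exclusion criterion leaves the gap open. A site that follows the synopsis and Section 12.2 can collect stool 21 to 27 days after the last dose, against 28 in Section 13.1.3. A site that follows Section 13.1.3 meets both rules.

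This assumes that 4 weeks means 28 days and that a dose exactly 28 days before the breath test is allowed. If that day counted as inside the exclusion period, the minimum would be 29 - 7 = 22 days. The number of children affected and the false-negative rate at 21 to 27 days are not in the documents, so the effect on agreement cannot be computed. The point should be corrected because it concerns an operative rule guarding against a source of error that the protocol itself names, and correcting it costs very little.

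**What to change.** 1. In the synopsis Study Procedure, replace the stool washout with the Section 13.1.3 rule: at least 2 weeks off proton pump inhibitors and H2 blockers, and 4 weeks off antimicrobials and bismuth.
2. In the exclusion lists of the synopsis and Section 12.2, tie the antibiotic and bismuth criterion to both the breath test and the stool antigen test, as the acid-suppressant criterion already is.
3. At the stool visit, compare last-dose dates with the stool date, using the medication history already recorded from 6 weeks back.

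Item 1 removes the contradiction, item 2 closes the gap in eligibility, and item 3 makes explicit a check that the existing data already support.

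The cost is a wording amendment, with no new procedure or data. A child whose last dose was 28 to 34 days before the breath test may have to give stool up to 7 days later than now allowed. The earliest compliant stool day is 28 - L relative to the breath test, which runs from day 0 (L = 28) to day -6 (L = 34). Every eligible child can comply within the existing window of 7 days either side.
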